8.10. Health Economics

Not applicable.

9. Statistical Considerations

9.1. Statistical Hypotheses

Formal statistical hypothesis testing is not planned. Therefore, adjustments for multiple testing do not apply.

9.2. Sample Size Determination

A maximum of 36 participants will be enrolled to study intervention with the intention that at least 6 participants randomized to LY3819253 have sufficient evaluable data in each of Cohorts 1 and 2.

This would mean at least 12 participants with evaluable data if Cohorts 1 and 2 only are enrolled. If the optional Cohort 3 is used, the total number of participants in the study with evaluable data will depend on enrollment numbers for that cohort.

The sample size is not powered on the basis of statistical hypothesis testing. However, based on an assumption of 40% CV for between subject variability in a PK parameter of interest, 6 subjects on active treatment per cohort may provide approximately 70% chance to ensure that a PK parameter's 90% confidence interval falls within (0.7, 1.43) over the corresponding geometric mean, such as AUC(0-∞).

A participant will be considered evaluable when the participant completes up to 29 days of study procedures. When a participant does not complete up to 29 days of study procedures, the sponsor will be consulted if the participant will need to be replaced.

9.3. Populations for Analyses

The following populations are defined:

Population	Description
Entered	All participants who sign the ICF
Enrolled/Intent-to-Treat	All participants assigned to treatment, regardless of whether they received study treatment, or if they took the correct treatment. Participants will be analyzed according to the treatment group to which they were assigned.
Safety	All participants randomly assigned to study intervention and who received study intervention. Participants will be analyzed according to the intervention they actually received.
Pharmacokinetic Analysis	All treated participants who received study intervention and have sufficient evaluable PK samples.

Abbreviations: ICF = informed consent form; PK = pharmacokinetic.

9.4. Statistical Analyses

Statistical analysis of this study will be the responsibility of sponsor or its designee.

All tests of treatment effects will be conducted at a 2-sided alpha level of 0.1, unless otherwise stated, and all confidence intervals will be given at a 2-sided 90% level.

Any change to the data analysis methods described in the protocol will require an amendment only if it changes a principal feature of the protocol. Any other change to the data analysis methods described in the protocol, and the justification for making the change, will be described in the SAP and the clinical study report. Additional exploratory analyses of the data will be conducted as deemed appropriate.

The SAP will be finalized prior to unblinding and it will include a more technical and detailed description of the statistical analyses described in this section. This section is a summary of the planned statistical analyses of the most important endpoints including primary and key secondary endpoints.

9.4.1. General Considerations

Statistical analyses will be performed using SAS® Version 9.4 or higher.

For continuous measures, summary statistics will include sample size, mean, standard deviation, minimum, median, and maximum. For categorical measures, summary statistics will include the sample size, frequency count, and percentage.

For all safety analyses, baseline will be defined as the last evaluable value before dosing.

9.4.2. Primary Endpoint: Pharmacokinetics

Pharmacokinetic parameter estimates for LY3819253 will be calculated by standard noncompartmental methods of analysis.

The primary parameters for analysis will be AUC(0-∞) of LY3819253 following SC administration. Other noncompartmental parameters, such as half-life, t_{max} , apparent clearance, and volume of distribution following SC administration may be reported.

In addition to noncompartmental analysis, the data may be combined with data from other studies to be analyzed using non-linear mixed-effect modelling of the PK data. This model will enable estimation of mean and variability (variances) of LY3819253 PK parameters, including bioavailability, following SC administration and to investigate potential covariates explaining that variability.

9.4.3. Secondary Endpoint: Safety

9.4.3.1. Clinical Evaluation of Safety

All investigational product and protocol procedure AEs will be listed, and if the frequency of events allows, safety data will be summarized using descriptive methodology.

The incidence of AEs for each treatment will be presented by severity and by association with investigational product as perceived by the investigator. Adverse events reported to occur prior to randomization will be distinguished from those reported as new or increased in severity during the study. Each AE will be classified by the most suitable term from the medical regulatory dictionary.

All SAEs will be reported.

9.4.3.2. Statistical Evaluation of Safety

Safety parameters that will be assessed include safety laboratory parameters and vital sign measurements. The parameters will be listed, and summarized using standard descriptive statistics. Additional analysis will be performed if warranted upon review of the data.

9.4.4. Exploratory Endpoint: Injection Site Reaction Assessments

Injection site reactions will be listed and may be summarized by dose if data warrant.

9.5. Interim Analyses

No interim analyses are planned for this study. If an unplanned interim analysis is deemed necessary, the Lilly CP, CRP/investigator, or designee will consult with the appropriate medical director or designee to determine if it is necessary to amend the protocol.

9.6. Data Monitoring Committee (DMC)

Not applicable.

10. Supporting Documentation and Operational Considerations

10.1. Appendix 1: Regulatory, Ethical, and Study Oversight Considerations

10.1.1. Regulatory and Ethical Considerations

This study will be conducted in accordance with the protocol and with the following:

- Consensus ethical principles derived from international guidelines including the Declaration of Helsinki and Council for International Organizations of Medical Sciences International Ethical Guidelines
- Applicable ICH GCP Guidelines, and
- Applicable laws and regulations.

The protocol, protocol amendments, ICF, IB, and other relevant documents (for example, advertisements) must be submitted to an IRB/IEC by the investigator and reviewed and approved by the IRB/IEC before the study is initiated.

Any amendments to the protocol will require IRB/IEC approval before implementation of changes made to the study design, except for changes necessary to eliminate an immediate hazard to study participants.

The investigator will be responsible for the following:

- Providing written summaries of the status of the study to the IRB/IEC annually or more frequently in accordance with the requirements, policies, and procedures established by the IRB/IEC
- Notifying the IRB/IEC of SAEs or other significant safety findings as required by IRB/IEC procedures, and
- Providing oversight of the conduct of the study at the site and adherence to requirements of 21 CFR, ICH guidelines, the IRB/IEC, and all other applicable local regulations.

Study sites are compensated for participation in the study as detailed in the clinical trial agreement.

10.1.2. Informed Consent Process

The investigator or their representative will explain the nature of the study, including the risks and benefits, to the participant or their legally authorized representative and answer all questions regarding the study.

Participants must be informed that their participation is voluntary. Participants or their legally authorized representative will be required to sign a statement of informed consent that meets the requirements of 21 CFR 50, local regulations, ICH guidelines, Health Insurance Portability and Accountability Act requirements, where applicable, and the IRB/IEC or study center.

The medical record must include a statement that written informed consent was obtained before the participant was entered in the study and the date the written consent was obtained. The

authorized person obtaining the informed consent and, if applicable, the individual designated to witness a verbal consent, must also sign the ICF.

Participants must be re-consented to the most current version of the ICF(s) during their participation in the study.

A copy of the ICF(s) must be provided to the participant or the participant's legally authorized representative and is kept on file.

10.1.3. Data Protection

Participants will be assigned a unique identifier by the sponsor. Any participant records, datasets or tissue samples that are transferred to the sponsor will contain the identifier only; participant names or any information that would make the participant identifiable will not be transferred.

The participant must be informed that their personal study-related data will be used by the sponsor in accordance with local data protection law. The level of disclosure must also be explained to the participant who will be required to give consent for their data to be used as described in the informed consent.

The participant must be informed that their medical records may be examined by Clinical Quality Assurance auditors or other authorized personnel appointed by the sponsor, by appropriate IRB/IEC members, and by inspectors from regulatory authorities.

The sponsor has processes in place to ensure data protection, information security, and data integrity. These processes include appropriate contingency plan(s) for appropriate and timely response in the event of a data security breach.

10.1.4. Dissemination of Clinical Study Data

A clinical study report will be provided for this study and a summary of study information provided on publicly available websites.

10.1.5. Data Quality Assurance

Investigator responsibilities

All participant data relating to the study will be recorded on printed or electronic CRF unless transmitted to the sponsor or designee electronically (for example, laboratory data). The investigator is responsible for verifying that data entries are accurate and correct by physically or electronically signing the CRF.

The investigator must maintain accurate documentation (source data) that supports the information entered in the CRF. Source data may include laboratory tests, medical records, and clinical notes.

The investigator must permit study-related monitoring, audits, IRB/IEC review, and regulatory agency inspections and provide direct access to source data documents.

Data monitoring and management

The Monitoring Plan includes

- monitoring details describing strategy, for example, risk-based initiatives in operations and quality such as risk management and mitigation strategies and analytical risk-based monitoring
- methods
- responsibilities
- requirements
- handling of noncompliance issues, and
- monitoring techniques.

The sponsor or designee is responsible for the data management of this study including quality checking of the data. The sponsor assumes accountability for actions delegated to other individuals (for example, contract research organizations).

Study monitors will perform ongoing source data verification to confirm that data entered in the CRF by authorized site personnel are accurate, complete, and verifiable from source documents. They will also ensure that the safety and rights of participants are being protected, and that the study is being conducted in accordance with the currently approved protocol and any other study agreements, ICH GCP, and all applicable regulatory requirements.

Records retention and audits

Records and documents, including signed ICFs, pertaining to the conduct of this study must be retained by the investigator for the time period outlined in the clinical trial agreement unless local regulations or institutional policies require a longer retention period.

No records may be destroyed during the retention period without the written approval of the sponsor. No records may be transferred to another location or party without written notification to the sponsor.

The sponsor or its representatives will periodically check a sample of the participant data recorded against source documents at the study site. The study may be audited by the sponsor or its representatives, and by regulatory agencies at any time. Investigators will be given notice before an audit occurs.

Data Capture System

The investigator is responsible for ensuring the accuracy, completeness, legibility, and timeliness of the data reported to the sponsor.

An EDC system will be used in this study for the collection of CRF data. The investigator maintains a separate source for the data entered by the investigator or designee into the sponsor-provided EDC system. The investigator is responsible for the identification of any data to be considered source and for the confirmation that data reported are accurate and complete by signing the CRF.

Data collected via the sponsor-provided data capture systems will be stored at third parties. The investigator will have continuous access to the data during the study and until decommissioning of the data capture systems. Prior to decommissioning, the investigator will receive an archival copy of pertinent data for retention.

Data managed by a central vendor, such as laboratory test data, will be stored electronically in the central vendor's database system and reports will be provided to the investigator for review and retention. Data will subsequently be transferred from the central vendor to the sponsor data warehouse.

Data from complaint forms submitted to the sponsor will be encoded and stored in the global product complaint management system.

10.1.6. Source Documents

Source documents provide evidence for the existence of the participant and substantiate the integrity of the data collected. Source documents are filed at the investigator's site.

Data reported on the CRF that are transcribed from source documents must be consistent with the source documents or the discrepancies must be explained. The investigator may need to request previous medical records or transfer records, depending on the study. Current medical records must be available.

The definition of what constitutes source data can be found in Section [10.1.5](#).

10.1.7. Study and Site Start and Closure

The study start date is the date on which the clinical study will be open for recruitment of participants.

Site Closure

The sponsor designee reserves the right to close the study site or terminate the study at any time for any reason at the sole discretion of the sponsor. Study sites will be closed upon study completion. A study site is considered closed when all required documents and study supplies have been collected and a study-site closure visit has been performed.

The investigator may initiate study-site closure at any time, provided there is reasonable cause and enough notice is given in advance of the intended termination.

Reasons for the early closure of a study site by the sponsor or investigator may include but are not limited to

- failure of the investigator to comply with the protocol, the requirements of the IRB/IEC or local health authorities, the sponsor's procedures, or GCP guidelines
- inadequate recruitment of participants by the investigator, or
- discontinuation of further study intervention development.

If the study is prematurely terminated or suspended, the sponsor shall promptly inform the investigators, the IECs/IRBs, the regulatory authorities, and any contract research organization(s) used in the study of the reason for termination or suspension, as specified by the applicable regulatory requirements. The investigator shall promptly inform the participants and assure appropriate participant therapy and/or follow-up.

10.1.8. Publication Policy

In accordance with the sponsor's publication policy, the results of this study will be submitted for publication by a peer-reviewed journal if the results are deemed to be of significant medical importance.

10.1.9. Investigator Information

Physicians with a specialty in infectious disease, critical care, or pulmonary disease may participate as investigators.

10.1.10. Long-Term Sample Retention

Sample retention enables use of new technologies, response to regulatory questions, and investigation of variable response that may not be observed until later in the development of the intervention or after the intervention becomes commercially available.

This table describes the retention period for potential sample types.

Sample Type	Custodian	Retention Period after Last Participant Visit
Pharmacogenetics sample	Sponsor or designee	up to 15 years
Exploratory Biomarker Samples	Sponsor or designee	up to 15 years
PK sample	Sponsor or designee	up to 2 years
Immunogenicity (ADA) sample	Sponsor or designee	up to 15 years

10.2. Appendix 2: Clinical Laboratory Tests

- Clinical laboratory tests will be performed according to the SoA. Additional details are provided in the following table for specific laboratory tests.
- Additional tests may be performed at any time during the study as determined necessary by the investigator or required by local regulations.
- Pregnancy testing will be performed according to the SoA.
- The following table describes when the local or central laboratory will be used.
- If the local laboratory results are used to make either a study intervention decision or response evaluation, the results must be recorded in the CRF.
- Laboratory results that could unblind the study will not be reported to study sites or other blinded personnel.
- Protocol-specific requirements for inclusion or exclusion of participants are detailed in Section 5 of the protocol.
- Investigators must document their review of each laboratory safety report.

Clinical Laboratory Tests	Comments
Hematology	Assayed by local laboratory
Hemoglobin	
Hematocrit	
Erythrocyte count (RBCs - red blood cells)	
Mean cell volume	
Mean cell hemoglobin	
Leukocytes (WBCs - white blood cells)	
Differential	
Neutrophils, segmented	
Lymphocytes	
Monocytes	
Eosinophils	
Basophils	
Platelets	
Cell morphology (RBC and WBC)	
Clinical Chemistry	Assayed by local laboratory
Sodium	
Potassium	
Chloride	
Bicarbonate	
Total bilirubin	
Direct bilirubin	Record on Day -1 and repeat if significantly abnormal value
Alkaline phosphatase (ALP)	
Alanine aminotransferase (ALT)	
Aspartate aminotransferase (AST)	
Blood urea nitrogen (BUN)	
Creatinine	

Clinical Laboratory Tests	Comments
Uric acid	Record on Day -1 and repeat if significantly abnormal value
Total protein	
Albumin	
Calcium	
Phosphorus	
Random glucose	
Calculations	Completed locally
Hepatitis B surface antigen	
Hepatitis B surface antibody	
Hepatitis B core antibody (HBcAb)	
Hepatitis C antibody	
HIV	
SARS-Cov-2 viral infection determination	Local laboratory
SARS-Cov-2 point of care	
SARS-Cov-2 nasal or nasopharyngeal sample for research purposes	Day 1 sample assayed by Lilly-designated laboratory. Subsequent samples sent to Lilly-designated laboratory for analysis only if the SARS-Cov-2 point of care test performed in parallel is positive
SARS-Cov-2 serology	Assayed by Lilly-designated laboratory.
Urinalysis	Assayed by local laboratory
Specific gravity	
pH	
Protein	
Glucose	
Ketones	
Bilirubin	
Urobilinogen	
Blood	
Nitrite	
Microscopy	If dipstick test is abnormal.
Hormones (female)	Assayed by local laboratory.
Serum pregnancy	
Urine pregnancy	
Ethanol/drug screening	Assayed by local laboratory.
Urine or breath ethanol screen	
Urine drug screen	
Pharmacokinetic (PK) Samples	Assayed by Lilly-designated laboratory. Results will not be provided to the study sites.
Pharmacogenetic sample	Assayed by Lilly-designated laboratory. Results will not be provided to the study sites.
Exploratory Biomarker Serum Sample	Assayed by Lilly-designated laboratory. Results will not be provided to the study sites.

Abbreviations: HIV = human immunodeficiency virus; SARS-Cov-2 = severe acute respiratory syndrome coronavirus 2.

10.2.1. Blood Sampling Summary

This table summarizes the approximate number of venipunctures and blood volumes for all blood sampling (screening, safety laboratories, and bioanalytical assays) during the study.

Purpose	Blood Volume per Sample (mL)	Number of Blood Samples	Total Volume (mL)
Screening tests ^a	45	1	45
Clinical laboratory tests ^a	15		
SARS-CoV-2 serology	10	5	50
Pharmacokinetics	4	12	48
Immunogenicity	10	5	50
Blood discard for cannula patency	1	5	5
Pharmacogenetics	10	1	10
Serum for exploratory biomarkers	10	6	60
Total			268
Total for clinical purposes (rounded up to nearest 10 mL)			270

^a Additional samples may be drawn if needed for safety purposes.

10.3. Appendix 3: Adverse Events: Definitions and Procedures for Recording, Evaluating, Follow-up, and Reporting

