AE review	X	X	Predose	X	X	X	X	X	X	X	X	X	X	AEs to be reviewed only after participant has signed the study ICF.
HIV, hepatitis B/C serology	X													

Procedure / Assessments	Screening	Treatment Period								Follow-up Visits				Comment
Visit Number	V1	V2								V3	V4	V5	V6/ED	
Week(s)		0								2	4	8	12	
Study Day	-14 to -1	-1	1	2	3	4	5	6	7	15 ±2d	29 ±3d	60 ±3d	85 ±3d	
Pregnancy test (women only) ^b	X	X											X	Serum pregnancy test at screening, urine test at other timepoints. Day -1 urine test refers to test at admission; this is not needed if admissions is on the same day as screening. Postdose urine test(s) can be performed at the judgment of the investigator, if pregnancy is suspected.
Clinical laboratory tests ^a	X	X							X	X	X	X	X	Fasting is not required for these tests. If screening takes place on Day -1, there is no need to conduct these tests twice on Day -1.
Breath or urine ethanol screen		X												Ethanol screen may be repeated at other time points at the discretion of the investigator.
Urine drug screen	X	X												Day -1 urine test refers to test at admission; this is not needed if admission occurs on the same day as screening. Drug screen may be repeated at other time points at the discretion of the investigator.

Procedure / Assessments	Screening	Treatment Period								Follow-up Visits				Comment
	Visit Number	V1	V2								V3	V4	V5	
Week(s)		0								2	4	8	12	
Study Day	-14 to -1	-1	1	2	3	4	5	6	7	15 ±2d	29 ±3d	60 ±3d	85 ±3d	
SC LY3819253 or placebo dosing			X											
LY3819253 PK sampling ^a			X	X	X	X	X	X	X	X	X	X	X	Day 1 collection should be taken up to 4h postdose ±4h. The exact time of draw must be recorded. For Day 2 onwards, PK samples may be taken at any time after vital signs.
Injection site assessments			Predose; 1min ±1min, 10min ±2min, 30min ±5min, 240min ± 10min	24h ±4h	X	X	X	X	X	X	X	X	X	Timepoints include ISR assessment, VAS, if pain is reported, and the exploratory Scarletred tool. Scarletred timing is flexible and not confined to the windows shown, except for predose. See Section 8.2.5 for detail.
Immunogenicity			Predose							X	X	X	X	
Serum sample for exploratory biomarkers ^a			Predose		X					X	X	X	X	
Pharmacogenetics sample ^a			Predose											For storage only.

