8.5. Pharmacokinetics

Venous blood samples will be collected as specified in the SoA for determination of serum concentrations of LY3819253 used to evaluate the PK for LY3819253.

A maximum of 5 samples may be collected at additional time points during the study, if warranted and agreed upon between the investigator and the sponsor.

Instructions for the collection and handling of biological samples will be provided by Lilly.

Site personnel will record

- the date and time (24-hour clock time) of investigational drug administration, and
- the date and time (24-hour clock time) of each PK sample.

It is essential that the times are recorded accurately.

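### The protocol's blood-volume total of 268 mL (270 mL rounded) includes none of the post-screening clinical laboratory draws and is about 90 mL too low

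*Protocol*

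**What the plan says.** Protocol section 10.2.1 states its own scope: the table gives the "approximate number of venipunctures and blood volumes for all blood sampling (screening, safety laboratories, and bioanalytical assays) during the study". Safety laboratories are therefore meant to be inside it.

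Each row has a volume per sample, a number of samples and a row total, for example "Screening tests ^a 45 1 45", "SARS-CoV-2 serology 10 5 50" and "Pharmacokinetics 4 12 48". The laboratory row reads only "Clinical laboratory tests ^a 15", with no number of samples and no row total. The table then gives a total of 268 mL and a last line, "Total for clinical purposes (rounded up to nearest 10 mL"), of 270 mL. Footnote a, attached to the screening and laboratory rows, allows further samples if safety requires them.

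The Schedule of Activities in section 1.3 marks clinical laboratory tests at screening, on Day -1 and on Days 7, 15, 29, 60 and 85. It allows one exception: "If screening takes place on Day -1, there is no need to conduct these tests twice on Day -1". Section 10.2 confirms that these tests follow the Schedule of Activities.

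**The concern.** A total that is said to cover safety laboratories should contain them. The blank cells in that row could be a loss in reading the PDF, so they prove nothing alone. What matters is whether the printed total leaves room for any laboratory volume.

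This table is the only place in the documents where the blood burden per participant is stated. The participants are healthy volunteers, and the ethics board and investigators would rely on the figure. An understated burden is a factual error in what they are told, even if the true volume is modest.

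**Working it through.** **1. Reproduce the printed total** (section 10.2.1; volume per sample × number of samples).

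| Row | Calculation | mL |
|---|---|---|
| Screening tests | 45 × 1 | 45 |
| SARS-CoV-2 serology | 10 × 5 | 50 |
| Pharmacokinetics | 4 × 12 | 48 |
| Immunogenicity | 10 × 5 | 50 |
| Cannula discard | 1 × 5 | 5 |
| Pharmacogenetics | 10 × 1 | 10 |
| Exploratory biomarkers | 10 × 6 | 60 |
| Sum without clinical laboratory row | | **268** |

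Rounded up to the next 10 mL this is 270. Both printed figures are reproduced exactly with a laboratory contribution of 0 mL.

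**2. Test whether lost cells could explain it.** One laboratory draw gives 268 + 15 = 283 mL. Any non-zero entry contradicts the printed total, so the conclusion does not depend on the blank cells.

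**3. Count the scheduled draws** (section 1.3). After screening: Day -1 and Days 7, 15, 29, 60 and 85, which is 6. If screening is on Day -1, the exception removes one, leaving 5. If the screening laboratory draw is not part of the 45 mL row, it must be added, giving 7.

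**4. Restate the total** as 268 + 15 × draws.

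| Reading | Draws | Omitted (mL) | Total (mL) | Rounded up (mL) |
|---|---|---|---|---|
| Base case: screening before Day -1, screening draw inside the 45 mL row | 6 | 90 | 358 | 360 |
| Screening on Day -1, screening draw inside the 45 mL row | 5 | 75 | 343 | 350 |
| Screening before Day -1, screening draw outside the 45 mL row | 7 | 105 | 373 | 380 |

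In the base case the printed total is 90/358 = 25% below the restated one.

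**5. Compare the other counts with the Schedule of Activities.**
- Serology: Day -1 and Days 15, 29, 60 and 85, which is 5. This agrees.
- Immunogenicity: predose and Days 15, 29, 60 and 85, which is 5. This agrees.
- Biomarkers: predose and Days 3, 15, 29, 60 and 85, which is 6. This agrees.
- PK: the table has 12. The schedule row shows Days 1 to 7, 15, 29, 60 and 85, which is 11 sampling days. The difference is 1 × 4 = 4 mL. With 11 samples the base case is 358 − 4 = 354 mL, which still rounds up to 360.

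**The case against.** The best defence is that the table is labelled approximate, that footnote a leaves safety sampling open, and that the number of laboratory draws varies. None of this accounts for the gap. An approximation does not cover the absence of a listed category. Footnote a concerns additional samples, not scheduled ones. The variation runs from five to seven draws and never reaches zero.

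Other objections do stand, and they limit the point:

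- **358 mL is not an established true total.** A reader might take it as one. The documents do not say whether the 45 mL screening row contains the screening laboratory draw, so 358 mL is a base case within a range. For the same reason the omission can be asserted only for the post-screening draws, not for every scheduled laboratory draw.
- **The PK count of 12 is not shown to be wrong.** A reader might infer that 11 is correct. Section 8.9 says that every immunogenicity time point coincides with a PK time point, and the Day 1 immunogenicity sample is predose. Read literally, this implies a predose PK sample besides the Day 1 postdose sample, which would make 12. The schedule row may be the incomplete side.
- **No limit is exceeded.** A reader might set the total against the 500 mL in exclusion criterion 30. That criterion concerns blood donated in the 3 months before screening; it does not cap study sampling, and the documents state no such cap.
- **The optional PK samples are not part of the error.** Section 8.5 says "A maximum of 5 samples may be collected at additional time points during the study", if warranted. They could add 5 × 4 = 20 mL, but a table of scheduled sampling may properly leave contingent samples out.
- **Nothing can be said about the consent form.** Consent pages are not among the material available, so no error there may be inferred.

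**Conclusion.** The table is wrong as written. Its total claims to include safety laboratories and contains no post-screening laboratory volume. The understatement is about 90 mL in the base case, with a range of 75 to 105 mL according to the day of screening and the content of the 45 mL row. The result rests on the table's 15 mL per sample and on the draws marked in the Schedule of Activities. It would fail only if one of those two were itself wrong.

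The consequence is confined to the stated burden on participants. Eligibility, dosing, endpoints and analyses are untouched. It is a correction that should be made, at the minor end of that category. The PK count is a separate inconsistency worth 4 mL that leaves the base-case rounded total at 360 mL.

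**What to change.** In section 10.2.1:

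1. Complete the clinical laboratory row from the Schedule of Activities: 6 samples and 90 mL, with a note that this is 5 samples and 75 mL when screening falls on Day -1.
2. State whether the 45 mL screening row includes the screening laboratory draw. If it does not, add 15 mL.
3. Reconcile the PK count between this table (12), the schedule row (11 sampling days) and section 8.9. Either show the predose PK sample in the schedule, or correct the table and section 8.9.
4. Restate the total and its rounded value, about 360 mL in the base case.
5. Check any participant-facing text that uses 268 or 270 mL, and update it if it does.

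The cost is a table correction and a less favourable stated figure. The laboratory schedule, design and analysis stay as they are.
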